4.1 Description of study design

This is an open-label, single arm, multi-center Phase IIIb study to evaluate the overall safety and tolerability and clinical efficacy of ribociclib in combination with letrozole in men and pre/postmenopausal women with HR+, HER2- aBC and no prior hormonal treatment for advanced disease. Gonadal suppression is achieved with either goserelin or leuprolide in men and premenopausal women patients.

The study will be composed of 2 phases:

- Core Phase: from FPFV to 18 months after LPFV. During the Core Phase, safety and efficacy data (including PROs in selected countries) will be collected;
- Extension Phase: from the end of the Core Phase to LPLV. In the event study patients are still deriving benefit at the end of the Core Phase and ribociclib is not approved or available and reimbursed, patients may be transitioned to this Extension Phase and continue to receive the drugs until progression, intolerance, death or physician/patient decision; only safety and clinical benefit (as assessed by investigator) data will be collected.

Approximately 3,000 patients across a diverse number of sites, countries, and regions are expected to be enrolled in this trial. Study treatment of the Core Phase will be provided until disease progression, death, unacceptable toxicities, physician's decision, subject/guardian's decision, protocol deviation, study termination by sponsor, lost to follow-up, technical problems or until 18 months after LPFV, whichever event occurs first (See Figure 4-1).

Enrollment in this trial is not competitive, with the purpose to include a diverse patient population in terms of sites, countries and regions. Each participating country will be assigned a predefined number of patients (based on number of participating sites and available patient population); once this number is achieved, countries may stop enrollment while the study will continue to enroll in other countries/regions. Safety data collected will include all AEs and SAEs including grade 3/4 AEs, events of special interest (Neutropenia including febrile neutropenia, QT prolongation, hepatobililary toxicity), AEs leading to permanent treatment discontinuation or death, vital signs, physical examination, variation of the ECOG performance status, and selected hematology/chemistry parameters at study visits while the patient remains on study and for 30 days after discontinuation.

Time to Tumor Progression (TTP) and overall tumor response (ORR/CBR) will be assessed by the investigator using RECIST v1.1 criteria. Tumor assessments should be performed every 12 weeks (recommended timeframe) or according to the current standard of care (as per local requirements) during treatment phase and at end of treatment (EOT). It is strongly recommended that a tumor assessment is performed before the patient is switched to a new antineoplastic therapy.

Local/regional sub-studies/analysis can be conducted in the patient population enrolled in [CLEE011A2404] (CompLEEment-1) study. These sub-studies can be designed to explore additional aspects of ribociclib treatment in HR+HER2- advanced breast cancer, which are not

assessed in the current CLEE011A2404 protocol. Examples of sub-studies include biomarker analysis (correlative science studies), additional patient-reported outcome (PRO) evaluations or any other relevant assessments that are not currently evaluated during CLEE011A2404 study. Sub-study protocols must follow the current Novartis process for review and approval of sponsored clinical trials, and should be reviewed and approved by the relevant regulatory authorities and Ethics Committees before implementation.

Figure 4-1 Study design

4.2 Timing of interim analyses and design adaptations

Interim analyses (IA) may be performed periodically. The first IA is planned to be performed about 12 months after FPFV, and periodically, if needed, to fulfill regulatory requests, safety updates, or for publication purposes.

4.3 Definition of end of study

Study recruitment will stop when approximately 3,000 patients are enrolled.

The planned overall study duration of the Core Phase will be from FPFV to 18 months after LPFV. At the time of Core Phase end if patients are still deriving clinical benefit and ribociclib is not approved or available and reimbursed, patients may be transitioned to the Extension Phase trial period and continue to receive the drugs until progression, intolerance, death or physician/patient decision, but only safety and clinical benefit as assessed by investigator will be collected during the Extension Phase.

The duration of the Extension Phase will be 18 months from LPLV of the Core Phase. During the Extension Phase, if ribociclib is approved and reimbursed, patients will be transitioned to prescription or drug access/support program(s) according to local laws and regulations.

The study will end after completion of the Extension Phase and all remaining patients will discontinue from the study. Patients who complete the Extension Phase, and continue to derive clinical benefit from the treatment based on the investigator's evaluation will receive ribociclib from prescription (if approved and reimbursed), another Post-Trial Access (PTA) program, or other drug access/support program(s).

Post-Trial Access (PTA) means the provision of treatment to trial participants following their completion of trial participation. PTA will be provided until one of the following is met: patient no longer derives clinical benefit, investigator discontinues treatment, launch or reimbursement (where applicable), treatment fails to achieve registration in the trial participant's country, or the clinical program is discontinued for any other reason.

The mechanism of PTA for this Extension Phase is provision of the Novartis investigational product in a non-trial setting (known as post-study drug supply [PSDS]) when no further safety or efficacy data are required, or any other mechanism appropriate for the country.

This PTA mechanism must comply with local laws and regulations in the participating trial countries. If Novartis discontinues the PSDS for this trial, Novartis will work with investigators to transition patients onto locally available alternative treatment, or standard of care.

The expected median follow-up at the time of study completion will be around 24 months, which is sufficient to provide adequate information about the safety and efficacy of ribociclib + letrozole in the population under investigation. According to data from Study CLEE011A2301 (MONALEESA-2), Grade 3/4 (G3/4) AE of special interest (neutropenia, QT prolongation and liver enzyme elevations) were observed during the first cycles of treatment (QTc prolongation observed during the first 2 cycles; 83.8% of the LFT elevations had been observed during the first 6 cycles; 85% of the G3/4 neutropenia events were observed during the first 12 months of treatment), so a minimal period of 18 months of follow-up seems sufficient to capture these events as part of the primary endpoint of the study. Additionally,

Amended Protocol Version 04 (Clean) Protocol No. Cl EE011A2	Novartis	Confidential	Page 50
	Amended Protocol Version 04 (Clean)		Protocol No. CLEE011A2404

patients entering in the Extension Phase will continue to have safety/tolerability monitored, which will generate relevant data about the long-term safety of this regimen.

4.4 Early study termination

The study can be terminated by Novartis at any time for any reason. This may include reasons related to the benefit/ risk assessment of participating in the study, practical reasons (including slow enrollment), or for regulatory or medical reasons. In taking the decision to terminate, Novartis will always consider the subject welfare and safety. Should early termination be necessary, subjects must be seen as soon as possible (provide instruction for contacting the subject, when the subject should stop taking drug, when the subject should come for a final visit) and treated as a prematurely withdrawn subject. The investigator may be informed of additional procedures to be followed in order to ensure that adequate consideration is given to the protection of the subject's interests. The investigator or sponsor depending on the local regulation will be responsible for informing IRBs/IECs of the early termination of the trial.

5 Population

5.1 Patient population

This trial will be conducted in men and pre/postmenopausal women with HR+, HER2- aBC who have not received any prior hormonal agent for the treatment of advanced disease.

Approximately 3,000 patients are expected to be enrolled in this trial.

Patients enrolled in this protocol are not permitted to participate in additional parallel investigational drug(s) studies while on treatment.

The investigator or designee must ensure that only patients who meet **all** the following inclusion and **none** of the exclusion criteria are offered treatment in the study.

5.2 Inclusion criteria

Patients eligible for inclusion in this study have to meet **all** of the following criteria:

- 1. Patient is an adult, male or female \geq 18 years old at the time of informed consent
- 2. Male or female advanced (locoregionally recurrent or metastatic) breast cancer not amenable to curative therapy.
- 3. In the case of women, both pre/perimenopausal and postmenopausal patients are allowed to be included in this study; menopausal status is relevant for the requirement of goserelin or leuprolide to be used concomitantly with ribociclib and letrozole.
 - a. Postmenopausal status is defined either by:

1. Prior bilateral oophorectomy OR

2. Age ≥ 60

OR

3. Age < 60 and amenorrhea for 12 or more months (in the absence of chemotherapy, tamoxifen, toremifen, or ovarian suppression) and FSH and estradiol in the postmenopausal range per local normal range. If patient is taking tamoxifen or toremifene and age < 60, then FSH and plasma estradiol levels should be in postmenopausal range per local normal range (NCCN Guidelines Version 2.2017).

Confidential

Note: For women with therapy-induced amenorrhea, serial measurements of FSH and/or estradiol are needed to ensure menopausal status.

- b. Premenopausal status is defined as either:
 - 1. Patient had last menstrual period within the last 12 months,

OR

2. If on tamoxifen or toremifene within the past 14 days, plasma estradiol and FSH must be in the premenopausal range per local normal range,

OR

- 3. In case of therapy induced amenorrhea, plasma estradiol and/or FSH must be in the premenopausal range per local normal range.
- c. Perimenopausal status is define as neither premenopausal nor postmenopausal

Note: Throughout this document, perimenopausal and premenopausal status is grouped together and referred as "Premenopausal"

- 4. Patient has a histologically and/or cytologically confirmed diagnosis of estrogen-receptor positive and/or progesterone receptor positive breast cancer by local laboratory. A confirmatory biopsy is not required.
- 5. Patient has HER2-negative breast cancer defined as a negative *in situ* hybridization test or an IHC status of 0, 1+ or 2+. If IHC is 2+, a negative *in situ* hybridization (FISH, CISH, or SISH) test is required by local laboratory testing.
- 6. Patient has an Eastern Cooperative Oncology Group (ECOG) performance status ≤ 2
- 7. Patient has adequate bone marrow and organ function as defined by ALL of the following laboratory values (as assessed by local laboratory):
 - Absolute neutrophil count $\geq 1.5 \times 10^9/L$
 - Platelets $\geq 100 \times 10^9/L$
 - Hemoglobin $\ge 9.0 \text{ g/dL}$
 - Potassium, sodium, calcium corrected for serum albumin and magnesium within normal limits or corrected to within normal limits with supplements before first dose of the study medication
 - INR ≤ 1.5
 - Serum creatinine < 1.5 mg/dl or creatinine clearance ≥ 50 mL/min
 - In absence of liver metastases, alanine aminotransferase (ALT) and aspartate aminotransferase (AST) should be below $2.5 \times ULN$. If the patient has liver metastases, ALT and AST should be $< 5 \times ULN$.
 - Total bilirubin < ULN except for patients with Gilbert's syndrome who may only be included if the total bilirubin is $\leq 3.0 \times$ ULN or direct bilirubin $\leq 1.5 \times$ ULN
- 8. Patient must have a 12-lead ECG with ALL of the following parameters at screening:
 - QTcF interval at screening < 450 msec (using Fridericia's correction)

- Resting heart rate \geq 50 bpm
- 9. Patient must be able to swallow ribociclib and letrozole tablets
- 10. Patient has signed informed consent obtained before any trial-related activities and according to local guidelines
- 11. Patients must be able to communicate with the investigator and comply with the requirements of the study procedures

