6.1.1 Dosing regimen

Ribociclib (LEE011) will be given orally once a day on days 1-21 of each 28- day cycle. On days 22-28 ribociclib will not be given ("rest days"). Letrozole will be given orally as per SmPC once a day on a continuous daily schedule (days 1-28 of each 28- day cycle). There will be no "rest" in the letrozole schedule. For men and premenopausal women, either goserelin will be given as an injectable subcutaneous implant or leuprolide will be given as an intramuscular injection. Either goserelin or leuprolide is recommended to be administered on day 1 starting at Cycle 1 and then every 28 days. Goserelin or leuprolide must be given as the monthly injection dosage form, as the 3-month depot dosage forms do not reliably suppress hormonal levels in all patients (NCCN ver. 2 2017). If a patient is already receiving goserelin or leuprolide before C1D1, a 28 days schedule should be maintained based on the pre-existing dosing schedule.

Table 6-1 Dose and treatment schedule			
Study treatments	Pharmaceutical form and route of administration	Dose	Frequency and/or Regimen
Ribociclib	Tablet for oral use	600 mg (3 tablets of 200 mg)	Daily on D1-D21 (28 day cycles)
Letrozole	Tablet for oral use	2.5mg	Continuous Daily
Goserelin	Injectable Subcutaneous implant	3.6 mg	Every 28 days (only for men and premenopausal women)
Leuprolide	Injectable Intramuscular Depot	7.5 mg	Every 28 days (only for men and premenopausal women)

See Table 6-1 and Figure 6-1 for details.

Figure 6-1 Men / Premenopausal regimen

* One cycle is 28 days unless modified due to AEs

Figure 6-2 Postmenopausal regimen

* One cycle is 28 days unless modified due to AEs

The study treatment will be administered as a flat-fixed dose (Starting doses: Ribociclib 600 mg QD 3 weeks on/1 week off; letrozole 2.5 mg QD continuously), and not by body weight or body surface area.

The investigator or responsible site personnel should instruct the patient to take the study treatment as per protocol (emphasizing the importance of compliance). Drug accountability must be performed on a regular basis. Patients will be instructed to return unused study treatment to the site at the end of each cycle. The site personnel will ensure that the appropriate dose of each study treatment is provided at each visit.

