7.2.2.5.4 Pregnancy and Hormonal Levels

Pregnancy tests are to be performed according to the Visit Evaluation Schedules outlined in Table 7-1 and Table 7-2

A positive urine test is required to be confirmed by an immediate serum pregnancy test.A positive pregnancy test requires immediate interruption of study treatment until the assessment is confirmed. If positive, the patient must be discontinued from the study.

FSH and estradiol will be collected locally and used for screening and confirmation of menopausal status and clinically monitored as indicated. FSH and estradiol results are not recorded in the eCRF.

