#### 2.2.6 Subgroup of interest

The following subgroups of interest may be used at interim and/or final analysis:

- Region (Latin American, Region Europe, Asia)
- Country (countries with at least 100 patients including, but not limited to US, Canada, Italy, Spain, France, Belgium, Czech Republic)
- Prior treatments for advanced disease (no treatments vs. chemotherapy)

Novartis	Confidential	Page 19
SAP	22-Feb-2022 (1:27)	CLEE011A2404

- Prior treatments for (neo)adjuvant (no treatments, endocrine only, chemotherapy only, both endocrine and chemotherapy )
- ECOG PS (PS 0-1 and 2)
- Liver involvement (yes vs. no)
- Lung involvement (yes vs. no)
- Lung or liver involvement (yes vs. no)
- Bone lesion only metastasis
- Other visceral/soft tissue involvement (adrenal, kidney, lymphonodes/soft tissue, etc.)
- Number of metastatic sites  $(0, 1, 2, \ge 3)$
- Age (<65, 65-<70, 70-<75, ≥75 years)
- Gender (male and female)
- Race (Asian vs. Non-Asian)
- Hormonal status at baseline (premenopausal vs. postmenopausal)

The objectives for carrying out analyses on these subgroups are to describe/characterize the treatment effect in these subgroups, to identify potential safety issues that may be limited to a subgroup of patients, or safety issues that are more commonly observed in a subgroup of patients.

With exception of male, summary tables will only be performed if at least 100 patients are present in each subgroup.

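### Criterion 3 lets the same woman qualify as both postmenopausal and premenopausal, and no rule says which status applies

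*Protocol*

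**What the plan says.** Protocol Section 5.2, criterion 3 (repeated in the Protocol summary), explains why status matters: "menopausal status is relevant for the requirement of goserelin or leuprolide to be used concomitantly with ribociclib and letrozole".

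- **3a, postmenopausal, any one of three routes.** The first is "Prior bilateral oophorectomy OR" the next item, which is age 60 or over. The third is for women under 60: at least 12 months of amenorrhea without certain drugs, plus FSH and estradiol in the postmenopausal range. A second sentence is attached to it: "If patient is taking tamoxifen or toremifene and age < 60, then FSH and plasma estradiol levels should be in postmenopausal range" by local limits.
- **3b, premenopausal, any one of three routes.** These are "Patient had last menstrual period within the last 12 months"; tamoxifen or toremifene in the past 14 days with both hormones in the premenopausal range; or therapy-induced amenorrhea with estradiol and/or FSH in that range.
- **3c.** "Perimenopausal status is define as neither premenopausal nor postmenopausal". Perimenopausal women are then grouped with premenopausal women.

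In Protocol Table 6-1 the LHRH agonist is given "Every 28 days (only for men and premenopausal women"). Tables 7-1 and 7-2 and Section 7.2.2 limit pregnancy testing to premenopausal patients. Protocol Section 10 and SAP Section 2.2.6 both list a two-level subgroup, in the SAP "Hormonal status at baseline (premenopausal vs. postmenopausal"). Protocol Section 7.2.2.5.4 adds that "FSH and estradiol results are not recorded in the eCRF".

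**The concern.** A classification that selects part of the regimen should put each patient in exactly one class. Here the lists were written separately. Item 3c closes the gap between them but does not deal with the overlap. A woman who meets both lists is, by the text, someone who should receive an LHRH agonist and also someone who should not.

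Three things depend on how the site resolves this: her gonadal suppression, her pregnancy testing, and her place in the pre/post subgroup. The SAP gives no derivation for the subgroup variable, so it does not settle the matter at analysis either.

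**Working it through.** The plan states no figure here to reproduce. The check is logical: take each postmenopausal route with each premenopausal route and ask whether one woman can satisfy both as written. All inputs come from criterion 3.

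| Postmenopausal route | b1: menses in past 12 months | b2: recent tamoxifen/toremifene, both hormones in premenopausal range | b3: therapy-induced amenorrhea, either hormone in premenopausal range |
|---|---|---|---|
| a1: bilateral oophorectomy | both | both | both |
| a2: age 60 or over | both | both | both |
| a3, first sentence | no | no | no |
| a3, tamoxifen sentence, amenorrhea also required | no | no | no |
| a3, tamoxifen sentence as a separate route | both | no | no |

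Routes a1 and a2 carry no condition on menses or hormones, and b1 to b3 carry no condition on age or surgery. That gives 2 × 3 = 6 overlapping pairs. Reading the tamoxifen sentence as a separate route adds one, making 7.

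A full enumeration agrees. Seven two-level facts were used: oophorectomy, age 60 or over, menses within 12 months, tamoxifen/toremifene use, therapy-induced amenorrhea, estradiol range and FSH range. They give 2^7 = 128 combinations.

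- Amenorrhea also required in the tamoxifen sentence: 30 postmenopausal only, 23 premenopausal only, 6 neither, 69 both (sum 128).
- Tamoxifen sentence as a separate route: 30, 21, 6 and 71 (sum 128).

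These are counts of logical combinations, some of them clinically implausible. They are not patient frequencies.

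Concrete cases:

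1. Oophorectomy 6 months ago, last period 7 months ago: a1 and b1. This is the clearest realistic case.
2. Age 60 or over, last period 10 months ago: a2 and b1.
3. Age 60 or over, therapy-induced amenorrhea, estradiol in the premenopausal range: a2 and b3.
4. Under 60, on tamoxifen, last period 8 months ago, both hormones in the postmenopausal range: a3 and b1, on the separate-route reading only.

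On the tamoxifen sentence, both readings are open. It sits inside an item that begins with an amenorrhea condition, which suggests the condition carries over. But that condition is framed for women not on tamoxifen, which suggests a separate route. The text does not decide.

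No order of precedence appears elsewhere in the Protocol or SAP.

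What could be checked from data already held: date of birth, medical and surgical history, and prior antineoplastic therapy are collected (Protocol Section 7.1.2.3). Goserelin and leuprolide dosing goes to the clinical database (Tables 7-1 and 7-2). Age can therefore be derived, and oophorectomy, tamoxifen/toremifene use and LHRH agonist use should be identifiable. The routes that turn on FSH or estradiol (a3, b2, b3) cannot be rebuilt from the database.

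**The case against.** The case for leaving this alone has real content.

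- **Few women are likely to be affected.** Overlaps at age 60 or over are probably uncommon, and the tamoxifen case depends on a disputed reading. This stands.
- **Sites might not differ over a woman without ovaries**, since the Protocol's stated purpose for the LHRH agonist is to suppress ovarian function (Section 1.2.4). This is plausible, but the text does not say it. Exclusion 17 itself accepts oophorectomy alone as contraception only after hormone confirmation, a condition that 3a does not carry.
- **Safeguards exist.** Exclusion 17 covers every woman physiologically able to conceive, whatever her menopausal label. Hormones are used to confirm status and followed as clinically indicated. Serial measurements are called for after therapy-induced amenorrhea. This stands, and it limits the safety concern without removing the contradiction.
- **The analytic effect is small.** The primary endpoint is a pooled description with no hypothesis test, and the pre/post split is one of many optional subgroups. This stands.
- **Enrollment is complete.** New wording cannot change past assignments. This stands, although 415 patients moved to the Extension Phase, where LHRH treatment and pregnancy testing still depend on status.

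Three stronger inferences are tempting, and the documents do not support them. A reader might infer that regimens become mixed within each subgroup. They do not through this defect, because the site's label decides the regimen and the two move together; a regimen that contradicts the label would be a protocol deviation, which is a different problem. A reader might infer that the sponsor cannot audit the classification. In fact hormone values remain in source, and Protocol Section 9.2 requires full verification of adherence to the eligibility criteria. The limit applies only to rebuilding the hormone-dependent routes from the database. Finally, a reader might want to state what share of the premenopausal subgroup could move. Neither the number of women meeting both lists nor the size of that subgroup is given, so any percentage would be invented.

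**Conclusion.** The point holds as a contradiction between stated rules. Criterion 3 can assign one woman two statuses with opposite instructions on the LHRH agonist, and nothing in the Protocol or SAP resolves it. Six route pairs overlap on any reading, and seven if the tamoxifen/toremifene sentence is a separate route.

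The effect is confined to individual regimen, pregnancy testing and the pre/post subgroup. The number of women among the 3,246 treated cannot be computed from the documents and is probably small. The pooled primary safety summary does not use menopausal status and is unaffected.

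The statement that label and regimen move together assumes that the analysis uses the site's own classification. The SAP does not say so, and the baseline data listed in Protocol Section 7.1.2.3 do not name menopausal status. Nothing here implies that either classification, or either regimen, is the right one for a woman who meets both lists.

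**What to change.** **Protocol.** Reconcile 3a, 3b and 3c, in Section 5.2 and in the Protocol summary, so that each woman falls in exactly one category, with a stated rule for those who meet both lists. State whether the 12-month amenorrhea condition applies to the tamoxifen/toremifene sentence. The content of these rules is for the sponsor's clinical team.

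**SAP Section 2.2.6.** State how the pre/post variable is derived: the status recorded by the site, naming the field that holds it, cross-checked against age, oophorectomy in the surgical history, prior tamoxifen or toremifene, and goserelin or leuprolide dosing. Flag women identifiable from these data as meeting both lists. Show the pre/post subgroup tables with and without them, labelled as a sensitivity analysis. Note that the hormone-dependent routes cannot be re-derived from the database.

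**Cost.** A wording change, a short SAP paragraph, and one further set of subgroup tables from data already collected. It needs no retrospective collection of hormone values from sites. It cannot alter assignments already made, and it will miss women whose overlap shows only in the hormone results.
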